1.1 Summary

We propose to test our central hypothesis that readmission and post-discharge utilization in high risk medical and surgical patients can be reduced by using a vendor platform (PinpointIQ from the company physIQ) that involves wearable sensors (Vital Patch) that collect real-time, continuous ambulatory vital signs, a mobile device that collects patient reported outcomes and machine learning algorithms in the cloud that identify patients at risk of physiologic perturbation. Data from this vendor platform will be tied to operational workflows at NorthShore that involve a monitoring nurse who then conveys information to the clinical team as necessary in a cascading alert system. This is a three phase study.

1.2 Background and Significance

Hospital readmissions are common and costly and are increasingly being used as a metric for quality care. With the passing of the Affordable Care Act (ACA) hospital readmissions were targeted with the Hospital Readmission Reduction Program (HRRP) in which hospitals are penalized for higher than expected readmission rates.¹ Significant effort has been devoted to understanding how to reduce readmissions and utilization. To date there has been limited work looking at how wearable sensors that monitor physiologic data continuously and remotely can identify physiologic perturbation allowing care providers ample time to intervene and prevent decompensation and readmission.

Monitoring of vital signs for hospitalized patients to detect decompensation is checked manually and intermittently (spot check) for the majority of patients. When patients are discharged, vital signs are frequently not monitored in the 30-day readmission window. This lack of monitoring in the post discharge period may prevent identification of patients at risk of decompensation and readmission. When spot vitals are monitored at home, reductions in readmission rates for certain populations have been seen.²⁻⁴

New technology in wearables coupled with machine learning algorithms is able to detect vital signs remotely and continuously and correlate the output with signals that may indicate risk of physiologic perturbation.⁵⁻¹⁷ Various studies have looked at how continuous monitoring of vitals can identify patients in the hospital quicker and more effectively than nurse driven spot checks of vital signs.¹⁸⁻²⁸ There is a lack of data on using these devices upon discharge to evaluate for decompensation and prospectively trying to reduce readmissions. Similarly, there is a lack of data in tying these devices to a cascading and escalating alert system to identify patients at risk of decompensation. There is qualitative data on looking at how wearables are perceived by providers and patients in the hospital²⁹⁻³⁰ but there is a lack of data on perception of this technology for remote monitoring.

Congestive heart failure (CHF) patients are frequently readmitted because of physiologic perturbation.³¹⁻³⁵ These populations have readmission rates between 15-30% at NorthShore. CHF patients are frequently readmitted because of exacerbations of their underlying heart failure.³¹⁻³² There has been early work establishing the predictive potential of multivariate physiological telemetry (pinpointIQ) from a wearable sensor providing accurate early detection of impending rehospitalization for CHF with a predictive accuracy comparable to implanted devices.³⁹ This population may benefit from remote continuous monitoring of vital signs tied to a cascading alert system to identify patients at risk of impending decompensation. There is limited literature looking at how continuous monitoring, ambulatory wearable devices can improve outcomes in high risk patients.

We propose conducting a mixed-methods study that will use a wearable device to collect ambulatory physiological data analyzed by a machine-learning algorithm to identify readmission risk. The alerts will be tied to a cascading escalation pathway that involves monitoring nurse, mid-level providers, specialists, and surgeons. We describe the quantitative and qualitative aspects of the study in detail below.

QUANTITATIVE

2.1 Quantitative Research Aims

Phase 1

Aim 1: Understand and finalize thresholds and criteria for alert system at the levels of Vital Patch, physIQ's pinpointIQ, monitoring RNs for CHF patients

Aim 2: Finalize process maps and workflows for nurse navigators and clinical care teams that optimize identifying high risk patients while minimizing provider burden

Phase 2

Aim 1: Determine if wearable technology deployed for 30 days in a high-risk patient population can augment 30-day readmission risk prediction and improve care processes via an escalating feedback protocol.

Aim 2: Calculate the return on investment of the remote monitoring solution

Aim 3: Perform a deep analysis of the full process to understand effectiveness, feasibility, efficiency and bottlenecks

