2.2 Experimental Plan and Methods

The goal of the study is to reduce readmission rates for high risk medical and surgical patients. Phase 1 will involve 5 high risk CHF patients. The goal of phase 1 is to understand how physIQ's platform Pinpoint IQ with a cascading set of alerts including the wearable device alerts, patient reported metrics, CAPE navigator or monitoring nurse alerts can be developed and improved upon to reduce the incidence of 30 day readmission. Phase 2 is the configuration and testing period before phase 3.

Phase 1

Phase 1 will assess the thresholds, process, and workflows of this cascading alert system. We will be enrolling 5 patients for this study at NorthShore University Health System.

CHF patients will be identified by an Enterprise Data Warehouse query that will report patients who meet specific inclusion and exclusion criteria daily. These criteria include being in the top 20% of the CAPE 30-day readmission risk prediction model, on the CHF service list at Evanston hospital, a patient of HF team, speaks English and does not have an implantable cardiomems device. The EDW query will be created and maintained by the clinical analytics team. These queries will be forwarded to the study coordinator who, when a qualifying patient is identified, will discuss with the CHF attendings regarding whether the patient is appropriate for this study. Patients will be approached by the study coordinator who will perform informed consent. If the patient is agreeable the patient will receive a kit from physIQ

prior to discharge. A Vital patch will be placed on the patient prior to discharge and the patch will be connected via blue tooth to the physIQ mobile device and pinpointIQ application. The study coordinator will teach the patient how to apply and remove the patch and what to do if there are issues with the patch. The study coordinator will also teach the patient how to use the mobile device and the physIQ application. The application will ask for the dry/current weight of the patient and this will be filled in prior to discharge.

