After discharge, CHF patients will be asked two questions every morning from the pinpoint IQ application. The pinpoint IQ platform will query patients about their current weight and if they actively have symptoms. These symptoms include chest pain, shortness of breath at rest, lightheadedness, dizziness, passing out, lower extremity swelling, orthopnea and postural nocturnal dyspnea. The monitoring nurse will evaluate the pinpoint IQ in the morning after the patient has filled out the questionnaire. They will evaluate the responses to the questions and the physiologic alerting system built by physIQ. There will be an algorithm built within physIQ's system that provides an alert to the monitoring nurse if the criteria from Table 1 are met.

Patients 1-5:
Any positive symptom
Example Question: Do you have any of the following symptoms? (multi-choice)
a. Chest pain b. Shortness of breath at rest c. Lower extremity edema d. Orthopnea (not able to lay flat) e. PND (Waking up in the middle of the night short of breath) f. Syncope (Passing out) g. Fatigue h. Vomiting i. Diarrhea
5 lb weight gain over dry weight (
Example Question:
What is your dry weight? What is your weight today?
A high risk alert
A predefined number of standard alerts in a day + 1-4 lb weight gain over dry weight

Table 1: Phase 1, physIQ alerts system for monitoring nurse for CHF

The actual thresholds for the high-risk alerts and the number of standard alerts may be changed from patient to patient based on how each case progresses and the density and frequency of alerts. Determining the optimal thresholds for these two types of alerts will be a key aim of phase 2. The goal is to maximize signal while minimizing noise.

If any of these conditions listed in Table 1 are met, the monitoring nurse will call the patient and go through a predefined note with the following data elements and questions.

monitoring nurse Alert System – CHF, phase 1

Do you currently have the following symptoms? (y/n)

- **Chest pain**
- **Shortness of breath at rest**
- Lower extremity edema
- Orthopnea (not able to lay flat)
- PND (Waking up in the middle of the night short of breath)
- **Syncope (Passing out)**
- Fatigue
- Vomiting
- Diarrhea

(Any Red Bolded symptoms results in phone call to clinical team and may physically see patients at home)

What is your dry weight? (Can look up patient's discharge weight and fill in or automate with data element)

What is your weight today? (Free text)

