Carnegie Mellon University (CMU) is a collaborating site and will have access to de-identified and date shifted patient and healthcare provider information. No HIPAA identifiers will be included in the data shared with CMU. Collaborators at CMU will be involved in developing and evaluating the 30-day readmission prediction model. Deidentified and date shifted data will be transferred to CMU over a Secure Sockets Layer (SSL) using a HIPAA compliant File Transfer Protocol (FTP). Data will be stored at NorthShore and at CMU on password-protected, encrypted computers. All research team members and graduate and doctoral students working with the data will complete Human Subjects Research certification. After completion of this project, all data at both NorthShore and CMU will be destroyed.

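### Phase 2 Aim 1 is worded for the wearable, but the comparison described measures the whole platform unless results are separated by signal source

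*Protocol*

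**What the plan says.** Protocol section 2.1, Phase 2 Aim 1, has two halves, both attached to the wearable. The first half reads "Determine if wearable technology deployed for 30 days in a high-risk patient population can augment 30-day readmission risk prediction". The second half turns from prediction to what follows an alert, and is to "improve care processes via an escalating feedback protocol".

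Section 2.2 describes what patients receive. They wear the patch, and each morning "The pinpoint IQ platform will query patients about their current weight and if they actively have symptoms". Table 1, labelled for Phase 1 and patients 1-5, lists four conditions that alert the monitoring nurse:

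- "Any positive symptom";
- "5 lb weight gain over dry weight";
- "A high risk alert";
- a set number of standard device alerts in a day together with a smaller weight gain.

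Any one of them leads to the same call and the same note template. The text after Table 2 lets new symptoms alone, or weight gain alone, change the diuretic dose.

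Section 4.6 gives the comparator: a retrospective usual-care sample from the 36 months before the study. It also refers to a predictive sub-aim as set out in the protocol, but no section sets it out. Section 5.1 says only that "Collaborators at CMU will be involved in developing and evaluating the 30-day readmission prediction model".

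The existing risk score, CAPE, appears as an eligibility criterion ("being in the top 20% of the CAPE 30-day readmission risk prediction model" in section 2.2; section 4.2.1 has a different cut-off, which does not matter here). It is not named as the benchmark for Aim 1.

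**The concern.** The aim names one component, but the design delivers several together. Self-reported symptoms and weight need no sensor, yet they open the same pathway as the device alerts. Suppose the platform predicts readmission better than the existing score, or nurses act sooner than in the historical sample. Either result could come from the patch, from two daily questions, or from both. As stated, the aim invites the reader to credit the patch.

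This matters because the results of Phases 1 and 2 are meant to inform the final process for Phase 3. A result labelled as the wearable's, but produced partly by the questions, would mislead that step.

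**Working it through.** The protocol gives no power calculation or accuracy target for Aim 1, so there is no figure to reproduce. Three checks follow.

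**1. Triggers by source (section 2.2, Table 1)**

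| Trigger | Needs an app answer | Needs the device |
|---|---|---|
| Any symptom | yes | no |
| 5 lb gain | yes | no |
| High-risk alert | no | yes |
| Standard alerts plus 1-4 lb gain | yes | yes |

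Two of four are patch-free, one is device-only and one is mixed. The count says nothing about how often each one fires.

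**2. Can the sources be separated?**

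Table 2 has separate fields for symptoms, weight change, and the number of high-risk and standard alerts. Section 5.2 lists physiologic, alert and patient-reported data as separate items returned to the site. So the increment of device data over app answers can be computed within the enrolled patients, without an app-only group.

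An illustration shows why the benchmark matters. The assumptions are mine: 200,000 simulated patients; three independent standard normal signals (risk score, app, patch); a logistic model with intercept -1.5 and risk-score coefficient 0.6; about 22% readmitted.

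| Coefficients (app, patch) | AUC: score | score + app | score + patch | all three | Gain over score | Patch step (all three minus score + app) |
|---|---|---|---|---|---|---|
| 0.8, 0 | 0.645 | 0.743 | 0.645 | 0.743 | 0.098 | 0.000 |
| 0, 0.8 | 0.647 | 0.647 | 0.745 | 0.745 | 0.098 | 0.098 |
| 0.5, 0.5 | 0.649 | 0.694 | 0.695 | 0.731 | 0.082 | 0.037 |

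The first two rows show the same gain over the risk score, although the patch contributes nothing in one and everything in the other. Only the last column tells them apart.

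**3. How precisely could the increment be estimated?**

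Inputs: 20 patients in total (section 4.3.1), 5 of them in Phase 1 (section 2.2), and readmission of 15-30% (section 1.2).

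- Expected readmissions: 20 × 0.15 = 3.0 to 20 × 0.30 = 6.0.
- If Phase 2 is the remaining 15: 15 × 0.15 = 2.25 to 15 × 0.30 = 4.5.
- Exact binomial probability of 10 or more readmissions in 20: 0.0002 at 15% and 0.048 at 30%.

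Hanley-McNeil standard error for an assumed AUC A, with n1 readmitted and n0 not: SE² = [A(1-A) + (n1-1)(q1-A²) + (n0-1)(q2-A²)] / (n1·n0), where q1 = A/(2-A) and q2 = 2A²/(1+A). For A = 0.70, q1 = 0.538 and q2 = 0.576.

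- 3 of 20 readmitted: SE = 0.182; approximate 95% interval 0.34 to above 1.
- 6 of 20 readmitted: SE = 0.137; approximate 95% interval 0.43 to 0.97.

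A single AUC is barely informative at this size, so a difference between two nested models cannot be tested usefully.

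**The case against.** The strongest reply is that the bundle is what the study declares it will assess. The central hypothesis in section 1.1 concerns a platform of sensors, patient reports and algorithms, and Phase 2 Aim 2 costs the remote monitoring solution as a whole. On that view the aim is only loosely worded. This stands in part, and it is why restating the aim for the platform is an acceptable fix.

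A second reply is that predictors, benchmarks and model form belong in a statistical analysis plan, which is not shown. That also stands, so the absence of a model specification is not the complaint. What remains is that the aim itself, which is protocol content, names the wearable, while the stated comparator has neither the study patch nor the app.

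Third, Table 1 is a Phase 1 table whose thresholds are expected to change. Carrying two of four into Phase 2 is an assumption, although the consent section commits all participants to answering survey questions for the whole study.

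A reader might go further and infer that no gain could ever be credited to the wearable. The documents do not support that: the signals are recorded by source, and one trigger needs the device alone. A reader might also infer that 30 days of wear doubles as the predictor window, so that alert totals are distorted by early readmission. No section specifies such a total. Alerts are counted by day or over the last 24 hours.

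**Conclusion.** The point holds as a mismatch between the wording of the aim and the comparison described. A difference in care processes from the retrospective sample, or a predictive gain from all platform data together, is a result for the bundle. It becomes a result for the wearable only if device data are set against a benchmark that already contains the symptom and weight answers.

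Three assumptions underlie this. CAPE is taken as the natural starting score because it is the only existing risk model named. The historical sample is taken to have had no study patch or app because it is usual care from before the study. The Phase 1 trigger structure is taken to carry forward in outline.

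On size: two of four triggers are patch-free, and 3 to 6 readmissions are expected among 20 patients. If these high-risk patients are readmitted more often than 15-30%, the count rises, but 20 patients still cannot support a formal comparison of nested models.

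One limit remains under any analysis. Alerts and symptoms both trigger care that may prevent the readmission being predicted, which affects the apparent accuracy of each.

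**What to change.** Choose one of two wordings for Phase 2 Aim 1:

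- state it for the whole remote monitoring platform; or
- keep it for the wearable and define its contribution as the increment of device alerts or the Multivariate Change Index over the existing risk score plus app symptom and weight answers, reported descriptively.

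Under either wording, add a field to the nurse note for which trigger or triggers prompted the call and which came first. Table 2 records symptoms, weight and alert counts but has no such field. Report the number of device-only calls, with mixed-trigger calls shown separately, and the lead time of device-only calls over the first later symptom or weight trigger. Because app answers are collected each morning, lead time is resolved to about a day. These summaries are informative even with few readmissions.

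The cost is a change of wording, one extra field and a little more analysis of data already captured. The wearable's apparent contribution may be smaller than a comparison of the whole platform would suggest. Lead times also remain affected by calls that change care before symptoms appear. No alert threshold or treatment rule needs to change.

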2.2 Experimental Plan and Methods

The goal of the study is to reduce readmission rates for high risk medical and surgical patients. Phase 1 will involve 5 high risk CHF patients. The goal of phase 1 is to understand how physIQ's platform Pinpoint IQ with a cascading set of alerts including the wearable device alerts, patient reported metrics, CAPE navigator or monitoring nurse alerts can be developed and improved upon to reduce the incidence of 30 day readmission. Phase 2 is the configuration and testing period before phase 3.

Phase 1

Phase 1 will assess the thresholds, process, and workflows of this cascading alert system. We will be enrolling 5 patients for this study at NorthShore University Health System.

CHF patients will be identified by an Enterprise Data Warehouse query that will report patients who meet specific inclusion and exclusion criteria daily. These criteria include being in the top 20% of the CAPE 30-day readmission risk prediction model, on the CHF service list at Evanston hospital, a patient of HF team, speaks English and does not have an implantable cardiomems device. The EDW query will be created and maintained by the clinical analytics team. These queries will be forwarded to the study coordinator who, when a qualifying patient is identified, will discuss with the CHF attendings regarding whether the patient is appropriate for this study. Patients will be approached by the study coordinator who will perform informed consent. If the patient is agreeable the patient will receive a kit from physIQ

prior to discharge. A Vital patch will be placed on the patient prior to discharge and the patch will be connected via blue tooth to the physIQ mobile device and pinpointIQ application. The study coordinator will teach the patient how to apply and remove the patch and what to do if there are issues with the patch. The study coordinator will also teach the patient how to use the mobile device and the physIQ application. The application will ask for the dry/current weight of the patient and this will be filled in prior to discharge.

After discharge, CHF patients will be asked two questions every morning from the pinpoint IQ application. The pinpoint IQ platform will query patients about their current weight and if they actively have symptoms. These symptoms include chest pain, shortness of breath at rest, lightheadedness, dizziness, passing out, lower extremity swelling, orthopnea and postural nocturnal dyspnea. The monitoring nurse will evaluate the pinpoint IQ in the morning after the patient has filled out the questionnaire. They will evaluate the responses to the questions and the physiologic alerting system built by physIQ. There will be an algorithm built within physIQ's system that provides an alert to the monitoring nurse if the criteria from Table 1 are met.

Patients 1-5:
Any positive symptom
Example Question: Do you have any of the following symptoms? (multi-choice)
a. Chest pain b. Shortness of breath at rest c. Lower extremity edema d. Orthopnea (not able to lay flat) e. PND (Waking up in the middle of the night short of breath) f. Syncope (Passing out) g. Fatigue h. Vomiting i. Diarrhea
5 lb weight gain over dry weight (
Example Question:
What is your dry weight? What is your weight today?
A high risk alert
A predefined number of standard alerts in a day + 1-4 lb weight gain over dry weight

Table 1: Phase 1, physIQ alerts system for monitoring nurse for CHF

The actual thresholds for the high-risk alerts and the number of standard alerts may be changed from patient to patient based on how each case progresses and the density and frequency of alerts. Determining the optimal thresholds for these two types of alerts will be a key aim of phase 2. The goal is to maximize signal while minimizing noise.

If any of these conditions listed in Table 1 are met, the monitoring nurse will call the patient and go through a predefined note with the following data elements and questions.

monitoring nurse Alert System – CHF, phase 1

Do you currently have the following symptoms? (y/n)

- **Chest pain**
- **Shortness of breath at rest**
- Lower extremity edema
- Orthopnea (not able to lay flat)
- PND (Waking up in the middle of the night short of breath)
- **Syncope (Passing out)**
- Fatigue
- Vomiting
- Diarrhea

(Any Red Bolded symptoms results in phone call to clinical team and may physically see patients at home)

What is your dry weight? (Can look up patient's discharge weight and fill in or automate with data element)

What is your weight today? (Free text)

Weight change over dry weight? (y/n or drop down)

- ≥ 5 lbs
- 1-4 lbs
- At or below dry weight

(Any Symptom + ≥ 5 lbs weight change over dry weight)

Diuretic Medication? (y/n)

- Are you on the same (standard) diuretic dose you were placed on at discharge or by your heart failure physician after an outpatient appointment?

(If on same medication and either new symptoms of shortness of breath at rest, lower extremity edema, orthopnea, PND or ≥ 5 lbs weight gain or 1-4 lbs weight gain with a prespecified number of standard alerts or a high risk alert than ask patient to double diuretic dose)

(If on double diuretic dose and no longer symptomatic AND back to dry weight, deescalate diuretic dose to discharge dose)

If you had symptoms yesterday are your symptoms better, worse, or the same today? (drop down for 4 choices: better, worse, same, N/A)

(If worse phone call to care team)

Med adherence? (y/n)

- Have you missed any diuretic doses in last 24h
- Have you missed any medication doses in last 24h

(Any symptom + not adherent to any meds) Reinforce importance of med adherence

Changes in diet, Salt intake? (y/n)

- Are you eating meals that you are making at home?

(Any symptoms + not eating meals that you are making at home) Reinforce importance of low salt diet and eating meals that you are making at home

Alerts over last 24 hours

- Was a high risk alert triggered (y/n)
- How many high risk alerts triggered: (Numerical answer)
- Were any standard alerts triggered (y/n)
- How many standard alerts triggered: (Numerical answer)

(High risk alert triggered)**Plan: (Multiple choice)**

- a. Phone call to clinical team for concerning symptoms
- b. Escalate or double diuretic dose
- c. Deescalate diuretic dose
- d. Reinforce med adherence
- e. Reinforce dietary adherence
- f. Other (free text)

Table 2: Phase 1, monitoring nurse nurse alerts system for clinical team for CHF

Table 2 will be configured into a note template within EPIC that allows for data elements to be captured. If any of the black or red bold logic is met the note will be forwarded to the clinical team with a high priority. If any of the red bolded elements are elicited from the patient, then the monitoring nurse will call the CHF clinical team for immediate communication. All notes will be forwarded to the clinical care team.

In addition, the monitoring nurse will double the diuretic dosing if a patient has new symptoms of shortness of breath at rest, orthopnea, postural nocturnal dyspnea, or lower extremity swelling. The double diuretic dosing will also occur if weight gain increases by ≥ 5 lbs over dry weight. If the symptom question is met, then the patient will get a 3rd question on Day n+1 that asks if the symptoms are getting better, worse or the same. If the symptoms are getting worse, the monitoring nurse will escalate to the clinical care team with a phone call. If the symptoms are getting better or are the same, the double dose of diuretic will remain unchanged. If symptoms or weight gain normalize, the double dose of diuretic will be deescalated to the standard dosing regimen.

If there is a high-risk alert, then the monitoring nurse receives an alert, which will result in a phone call to the patients and note template with patients. The monitoring nurse alert will also occur if there are a certain number of alerts (to be determined and varied during patients 1-5) and 1-4 lbs of weight gain (to be determined and varied during patients 1-5). In addition, if patients have some combination of weight gain and standard alerts or a high-risk alert, then the doubling of diuretics will also occur. If patients have a combination of 1-4 lb weight gain and a set number of device alerts, we will stop diuretic dosing if weight gain normalizes back to dry weight. The process map for patients 1-5 is shown in Figure 1. Escalating and deescalating diuretic dosing will also be built into the same note template in addition to prompts for education to ensure a standardized process from the monitoring nurses. We also have a multiple-choice option for monitoring nurse to document the care plan for participants.

[figure not shown]

Figure 1: Process map for CHF Patient 1-5

If care is escalated to the clinical care team which includes Advanced Practice Nurses, Physician Assistants and Physicians, the care team will pursue various interventions including counseling, altering medication therapy, urgent visits to heart failure clinic ideally within 72 hours, and if no other available options readmission. These workflows will be left to the discretion of the clinical care team given the nuance in taking care of these high-risk patients and the existing relationship and prior history with

these providers. There are some standardized workflows that will be followed by the care team that are of note. If the patient has diuretic dose escalated for 3 days, then the clinical care team will make sure patient has a basic metabolic panel ordered to make sure patient's renal function is stable on the higher diuretic dose. We created a standardized note template for mid-level providers as part of the escalation pathway (Table 3). Also, all messaging from the monitoring nurse will be forwarded to the heart failure clinical pool and/or CHF APP pool per protocol to create the most rapid response back to the patient if required.

Cardiovascular symptoms not related to CHF Is the patient having any concerning cardiovascular symptoms not related to CHF? (y/n)
Pulmonary symptoms Is the patient having any concerning pulmonary symptoms not related to CHF? (y/n)
Infectious symptoms Is the patient having any symptoms concerning for an infection (eg: fever, dysuria, productive cough, diarrhea, vomiting, rash, or flu-like symptoms)? (y/n)
Urine output Does the patient have decreased urine output or are they not responding to their diuretic dose? (y/n)
Hematologic symptoms (such as bleeding and thrombosis) Is the patient having any concerning hematologic symptoms? (y/n)
Medication adherence questions 
 • In the last week has the patient missed any diuretic doses (eg: lasix, bumex, spironolactone)? (y/n/na) • In the last week has the patient missed any beta blocker doses (eg: metoprolol, carvedilol)? (y/n/na) • In the last week has the patient missed any ACE/ARB doses (eg: enalapril, lisinopril, benazepril, captopril, quinapril, irbesartan, losartan, olmesartan, valsartan)? (y/n/na)
Self-Care 
 1. Did the patient ask any questions related to self-care? (y/n) 2. Did a family member or caregiver ask any questions related to self-care? (y/n) 3. Did the patient or a family member or caregiver know their medications? (y/n) 4. What led to your communication with the patient? (monitoring nurse recommendation, patient called, abnormal lab finding, other)
Assessment 
 1. What do you think is the cause of the patient's decompensation? (HF exacerbation, cardiovascular non-HF, pulmonary, infectious, renal, other) 2. On a scale of 1 to 5 how confident are you in this choice? 1 being least confident, 5 being extremely confident (select number 1-5 from drop down menu)
Plan 
 3. Plan? Please select all that apply from the following options (multi-select) 
 a. Continue PO diuretic

- b. Increase PO diuretic
- c. Decrease PO diuretic
- d. Hold PO diuretic
- e. Start IV diuretic
- f. Was there a change or new addition of a BB
- g. Was there a change or new addition of a ACEI/ARB/ARNI
- h. Was there a change or new addition of mineralocorticoid receptor antagonists (MRAs)
- i. Start antibiotic
- j. Start breathing treatment

Other interventions (not medication related)

- a. Have monitoring nurse do in person visit
- b. Set up cardiology urgent visit
- c. Send patient to the ER
- d. Check labs
- e. Check imaging
- f. Other (free text)

Table 3. Mid-level CHF Note Template

For phase 1 and 2 there will be significant data collection that is part of this process to understand how our process maps result in outcomes. Learnings from these 20 patients will inform the final process for phase 3 CHF.

QUALITATIVE

